### *Overview of trial visits*

#### 6.1 Screening Visit

A patient with an unruptured saccular intracranial aneurysm will be considered for participation in PROTECT-U if the benefits of preventive aneurysm treatment (by means of clipping or an endovascular procedure) do not outweigh the procedural risks, preferably according to a multidisciplinary team of physicians (which at least includes a neurosurgeon, an interventional neuroradiologist and a neurologist). The management decision is discussed with the patient at the outpatient clinic and is part of regular care. If the patient may be eligible for PROTECT-U, he/she will be informed and asked to provide informed consent (IC). To sign the IC form, the patient will be given sufficient time. During the screening visit, the patient will be screened for eligibility (in- and exclusion criteria) for PROTECT-U. The following are key elements of the screening visit:

- The trial will be explained to the patient and written information regarding the trial will be provided.
- Demographic data are collected as well as vital signs (blood pressure, height, weight).
- Medical history is obtained regarding inclusion- and exclusion criteria, concomitant medication, smoking status and alcohol consumption.
- If necessary, a blood sample for verification of inclusion/exclusion criteria is taken (pregnancy test for women with childbearing capacity, creatinine to permit a GFR-estimation as described above, see 4.5). The investigator may decide to include other parameters, if needed (e.g. INR, thrombocytes count, hemoglobin).
- Depending on the cycle and the time between the visits, this test should be repeated at the baseline visit.
- Screening logs will be collected at the trial centres which will include all patients screened for study participation. Reasons for non-eligibility will be collected.

Patients may be contacted prior to the visit to inform them about the PROTECT-U trial. Written information will then be mailed. In these situations, patients have sufficient time to consider participation in the trial, in case the multidisciplinary team decides against preventive

endovascular or neurosurgical treatment of the aneurysm. At their visit to the tertiary care facility, remaining questions will be answered. If the patient is interested in participation, they will be randomized at their first visit to the tertiary care facility (see 6.2) after informed consent has been obtained. Patients may also be provided with information about the trial and asked screening questions when scheduled for a standard of care visit, e.g. for imaging. If the informed consent has already been signed by patient at the time of the screening visit, blood samples (see 6.2) may be taken at this visit.

## 6.2 Baseline Visit

The following are key elements of the baseline visit:

- Confirmation that all inclusion- / exclusion criteria are satisfied
- If a recent (<6 months) GFR (determined at the lab of the trial center or at another lab that provides a copy of the appropriate lab certificate) is not available, a blood test will be done to measure GFR after informed consent has been obtained.
- Verification of participant contact information
- Completion of the study randomization procedure using an online randomization tool, as soon as lab values needed for inclusion (e.g. negative pregnancy testing) are available.
- Collection of the following baseline characteristics by history taking: history of hypertension / ischemic stroke / intracerebral hemorrhage / subarachnoid hemorrhage / myocardial infarction / peripheral vascular disease / polycystic kidney disease, tobacco smoking history including number of packyears of smoking and current number of cigarettes per day, medication use, alcohol consumption, number of first degree and second degree relatives with an intracranial aneurysm (either unruptured or ruptured), and an EQ-5D-5L questionnaire is completed by the patient.
- Collection of aneurysm characteristics based on reviewing medical data: 1) number of intracranial aneurysms; 2) anatomical site(s) of the UIA; 3) maximum UIA diameter; and 4) aneurysm shape.
- A blood pressure will be measured in sitting position.
- If the time between screening visit and baseline visit exceeds so much time (depending on the cycle of the patient) that another pregnancy test is necessary, an additional rapid test will be performed.
- Clinical chemical parameter may be controlled, if the investigator decides they are necessary.
- A baseline assessment for symptoms of potential adverse effects of ASA is performed prior to beginning the therapy.
- Trial medication is provided to patients randomized to the intervention group.
- Patients in the intervention arm will be provided with a letter to the treating physician explaining the study in detail and the blood pressure limits aimed for (120 mmHg systolic). Also a device for blood pressure measurements at home will be handed to the patient. The patient will be explained how to do measurements with this device. Patients provided with an electronic blood pressure measuring device are recommended to use this device to measure blood pressure at home at least once per week and up to 4 times per week, which will ensure that we do not exceed the maximum of 100 measurements at the time of each follow-up. However, if a patient would not do weekly measurements, this would not be defined as protocol deviation.

|   |   |                               |
|---|---|-------------------------------|
| Clinical Trial Code: Protect-U
EudraCT: 2017-000514-35 | Trial Protocol
Version 07 - August 23 - 2022 | Page 36 of 62
CONFIDENTIAL |
|---|---|-------------------------------|

The last routine imaging of the aneurysm (either CTA or MRA) within 3 months before randomization) will be uploaded to a central server in a pseudonymised manner by using the patient ID number and date of imaging. The pseudonymisation method must not reveal the allocation to intervention group or standard of care, to permit a blinded imaging assessment. Screening and Baseline visit may be performed at one single day.

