## 5.6 Blinding

This is an open trial, in which patients and investigators are not blinded. However, there will be an examiner-blinded assessment of images, therefore no information of patient allocation using patient ID-numbers or other data that would unblind the allocation of a patient to one of the two trial arms should be made available prior to the imaging analysis.

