### 9.3 Statistical Methods

Baseline characteristics will be summarized as means with standard deviations or proportions, as appropriate. In the primary analysis we will quantify the treatment effect of a strategy aimed at risk factor modification by intensive blood pressure treatment, monitoring with a blood pressure measuring device, and acetylsalicylic acid (ASA) on the risk of aneurysm rupture or growth, which is an established surrogate for the risk of rupture, compared with standard blood pressure treatment and no ASA.

We will compare the occurrence of outcome events in the two groups in terms of the risk ratio (RR), which will be obtained by means of a Poisson model. The precision of the RR estimates will be described with 95% confidence intervals obtained from the Poisson model. Our primary analyses will be based on the intention-to-treat principle. Patients will be censored in case of death from causes other than aneurysm rupture. In addition to crude analyses, we will do an analysis adjusted for the main risk factors of the primary outcome: aneurysm size, shape, location, age and smoking status. For our secondary analyses in which the timing of the outcome event is not prespecified but all follow-up data are taken into account, we will calculate hazard ratios using Cox regression analyses. Final details will be specified in the Statistical Analysis Plan.

We plan the following subgroup analyses: age ( $\leq 55$  versus  $> 55$  years), sex, and type (with or without previous rupture of another aneurysm), size (1.0-4.0 mm versus  $\geq 4.1$  mm), aneurysm location (posterior communicating artery / anterior communicating artery / posterior circulation versus all other aneurysms) and morphology of aneurysm (regular versus irregular shape).

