## 10 DATA MANAGEMENT

### 10.1 Data Collection

A study specific database will be set up using ClinCase™ and validated for this project with coded information of the participants who are included in the study. After informed consent, subjects will be registered in a secured database managed by the KKS using unique participant identification numbers. The patient ID is composed of a site number and the randomization number generated by the online randomizing tool. Only authorized study personnel will have access. Hence, the names and patient numbers of participants will be replaced by a study code for all study related procedures and will not be directly convertible to the participant. This code list is exclusively possessed by PI and investigators at each trial centre, and saved in a separate, secured database. All data will be collected according to the applicable national data protection, privacy and secrecy laws.

Study data collected in the e-CRF will consist of:

- Study characteristics: study number, date of randomization, treatment allocation.
- Data collected at baseline: date of birth, sex, history of hypertension / ischemic stroke / intracerebral hemorrhage / subarachnoid hemorrhage / myocardial infarction / peripheral vascular disease / polycystic kidney disease, medication use, tobacco smoking history including number of packyears of smoking and current number of cigarettes per day, alcohol use, recent (<6 months) GFR, number of first degree and second degree relatives with an intracranial aneurysm (either unruptured or ruptured), date and type of last aneurysm imaging before randomization, seated blood pressure, number of aneurysms, aneurysm size, aneurysm location, aneurysm shape, EQ-5D-5L.
- Data collected during the trial: smoking status, seated blood pressure, drug adherence (by counting unused tablets), occurrence of adverse events, concurrent medication, date(s) and type(s) of subsequent imaging, occurrence of aneurysm growth or rupture during trial according to local investigator, occurrence of cardio-/cerebrovascular outcomes during the trial, EQ-5D-5L.

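### Nothing requires baseline EQ-5D-5L, seated blood pressure or site-recorded aneurysm size and shape to be recorded before allocation in this open-label trial

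*Protocol*

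**What the plan says.** Section 6.2 of the protocol gives the key elements of the baseline visit as an unnumbered list. After eligibility, GFR and contact details comes "Completion of the study randomization procedure using an online randomization tool, as soon as lab values needed for inclusion" are available. Later items are history taking, at the end of which "an EQ-5D-5L questionnaire is completed by the patient"; "Collection of aneurysm characteristics based on reviewing medical data" (number, site, maximum diameter and shape); and "A blood pressure will be measured in sitting position".

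Section 5.6 states: "This is an open trial, in which patients and investigators are not blinded". Blinding is confined to the reading of images.

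The Clinical Trial Schedule enters the EQ-5D-5L, the aneurysm and baseline characteristics and the seated blood pressure for the first time at Visit 1, which is also the visit of randomisation. Section 10.1 lists the baseline items held in the eCRF, among them "seated blood pressure, number of aneurysms, aneurysm size, aneurysm location, aneurysm shape, EQ-5D-5L".

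Section 9.3 adjusts a supplementary analysis of the primary outcome for aneurysm size, shape, location, age and smoking status. Its subgroups include aneurysm size (cut between 4.0 and 4.1 mm) and "morphology of aneurysm (regular versus irregular shape"). The cost-effectiveness part of 9.3 relates cost differences to changes in quality of life, using the EQ-5D-5L.

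**The concern.** A baseline value is protected by randomisation only if it is fixed before anyone who can influence it knows the arm. Here the patient fills in the EQ-5D-5L, and the site takes the blood pressure and records size and shape from the medical data. Both may already know the allocation.

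The items differ in how much is at stake:

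- **EQ-5D-5L.** A patient who has just been assigned to the active strategy, or to no change in care, may answer differently for that reason. The answer then stands as the starting point for change in quality of life and for cost-utility.
- **Seated blood pressure.** Knowledge of a target below 120 mmHg in one arm can affect how a first reading is taken or repeated.
- **Size and shape.** Regular versus irregular is a judgement, and a diameter near the 4.0/4.1 mm cut can fall either way. If borderline cases were classified differently by arm, the subgroup results and the adjusted estimate could be distorted.

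**Working it through.** The sample size is not involved, but it reproduces. With 15% versus 8.25%, two-sided alpha 0.05, 80% power and mean rate (0.15 + 0.0825)/2 = 0.11625:

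n = [1.960 × √(2 × 0.11625 × 0.88375) + 0.8416 × √(0.15 × 0.85 + 0.0825 × 0.9175)]² / (0.0675)² = (0.8884 + 0.3794)² / 0.004556 ≈ 352.8, so 353 per group, as section 9.1 states. Collecting baseline data before allocation does not change this number.

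The point itself is settled by comparing the texts.

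**1. Is there a rule that puts these items before allocation?** The only stated trigger for randomising is availability of the laboratory values needed for inclusion (6.2). The one timing rule for a baseline assessment concerns symptoms of possible ASA side effects. It is tied to the start of therapy, not to allocation. No other section supplies a rule.

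**2. Are the items secured at an earlier visit?**

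| Item | Collected at screening? | Role in 9.3 |
|---|---|---|
| EQ-5D-5L | No | Quality-of-life change, QALYs |
| Seated blood pressure | A blood pressure is taken among the vital signs (6.1); the scheduled seated reading starts at Visit 1 | Neither adjustment nor subgroup variable |
| Aneurysm size, shape | Not scheduled as data; the scan exists | Adjustment and subgroup |
| Aneurysm location | Not scheduled as data; the scan exists | Adjustment and subgroup |
| Age | Yes, demographics | Adjustment and subgroup |
| Sex | Yes, demographics | Subgroup |
| Smoking status | Yes | Adjustment |

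Screening and baseline may fall on one day (6.2), which narrows the separation for the items that are collected at screening.

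**3. Does data entry point the same way?** Section 5.4.1 builds the patient study number from the centre code and the randomisation number. Section 10.1 registers subjects in the database under an ID composed in that way. Read literally, eCRF entry under that ID can begin only after randomisation. This fixes when data are entered, not when they are collected, but it means that the database gives no safeguard on order.

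**4. What would a shift do?** If learning the arm moves the mean baseline EQ-5D index by δ more in one arm than in the other, and later values are unaffected, the between-arm difference in change from baseline moves by the full δ in the opposite direction. The documents give no value for δ, so no size can be attached. The crude primary risk ratio contains no baseline covariate, so δ does not enter it.

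**The case against.** The strongest reply is that section 6.2 does not set a sequence. It is a list of key elements, and it is demonstrably not chronological: the repeat pregnancy test is listed after randomisation, although a negative test is named as a condition for randomising. A reader might infer that the protocol tells sites to randomise first and collect baseline data afterwards. The text does not support that; it only leaves the order open. This objection stands and limits the point to a missing rule.

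Four further inferences go too far:

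- **That baseline, adjustment and subgroup variables are all compromised.** Age and sex cannot move with the arm. Smoking status and one blood pressure are taken at screening. Blood pressure and EQ-5D-5L are neither adjustment nor subgroup variables.
- **That aneurysm size and shape are lost.** They are taken from existing records, the scan dates from the 3 months before randomisation, and it is uploaded for blinded assessment. They can be re-read blind. The protocol does not say whether site or central values enter the adjusted and subgroup analyses, and the SAP may properly settle that.
- **That the primary result is at risk.** The primary comparison is the crude intention-to-treat risk ratio, with growth and rupture read centrally by two blinded radiologists. The adjusted analysis is additional.
- **That a QALY bias can be stated.** For example, 3 years × an assumed baseline slope of 0.6 × an assumed shift of 0.01 to 0.03 gives 0.018 to 0.054. The slope and the shift are not in the documents, and 9.3 specifies no regression on baseline EQ-5D-5L.

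The objection leaves one fact standing: a site that follows the text can take the first EQ-5D-5L after the patient knows the arm.

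**Conclusion.** The point holds in limited form. Randomisation depends only on the inclusion laboratory values, and no rule places EQ-5D-5L, seated blood pressure or site-recorded size and shape before allocation. The exposure is real for the EQ-5D-5L, which is patient-reported, scheduled at no earlier visit and impossible to recover afterwards. It is smaller for seated blood pressure, and small for size and shape because the scans predate allocation. It touches the quality-of-life and economic results and, for borderline aneurysms, the adjusted and subgroup analyses; the crude primary analysis is untouched. Its size cannot be derived from the documents. The conclusion assumes that some sites do randomise before these items are recorded, which the protocol permits but does not report. It is worth acting on because the remedy is nearly free, and an SAP cannot restore a pre-allocation questionnaire that was never taken.

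**What to change.** Add to section 6.2: *EQ-5D-5L, seated blood pressure, history and aneurysm characteristics are completed and dated on source documents (under the screening number) before the randomisation tool is opened; eCRF entry may follow.*

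Requiring prior entry in the eCRF would not work as the database is described, because the patient ID contains the randomisation number. The screening number in 5.4.1 already exists for this purpose, and the EQ-5D-5L is already on paper (2.2).

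Preferably, state in 9.3 or the SAP that baseline size and shape for the adjusted and subgroup analyses come from the blinded central reading of the baseline scan, with site values used only if that reading is missing. The readers need the baseline scan to judge growth in any case; what is added is recording shape as well.

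The cost is a reordered visit checklist and one or two sentences. With last subject in planned for Q2 2026, the change protects patients enrolled after it takes effect. For those already randomised, size and shape can still be read blind, but the EQ-5D-5L cannot be retaken.

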### 6.3 Treatment Visits

Treatment visit schedules for data collection do not differ by group assignment. For the purpose of data collection and event ascertainment all participants will have post-randomization visits, at month 6 (+/- 30 days), and every 6 months (+/- 30 days) thereafter. During all treatment visits, blood pressures will be recorded in a sitting position. Patients will be asked for the occurrence of adverse events and (reasons) of admissions to hospitals and visits to outpatient clinics, quality of life (EQ-5D-5L), information regarding concomitant medication, and the cardiovascular outcome are retrieved. All subsequent CTAs/MRAs of the aneurysm which are made as part of standard care will be uploaded in a pseudonymised manner to a central server.

Patients of the intervention group will be asked to have the blood-pressure device with them, to permit a readout of the blood-pressure values to a tablet computer at the trial centre. In case patients did not yet transfer the blood pressure measurements to the central database using their own smartphone, the investigator can transmit available measurements in a pseudonymized fashion via a secure online connection to the central database at the sponsor's institution (University Medicine Mannheim). The investigator will see a displayed graph at the tablet computer and will categorize the findings into one of these three classifications:

- The blood pressure is satisfactory or lower,
- The blood pressure is higher than recommended,
- The blood pressure is not checked at least once a week

Based on the available blood pressure data, the investigator will decide whether or not the patient should see a GP for optimisation of blood pressure treatment. If the blood pressure is not checked at least once a week, patients are reinstructed how to use the device.

Blood pressure data obtained by the electronic device are not subject to clinical monitoring.

For the control group, a visit could be replaced by a telephone visit, if the previous visit was performed at the trial center.

In the event that the Covid-19 pandemia would cause circumstances in which the treatment visits need to be cancelled, the scheduled trial visit can be replaced by a telephone visit. The blood pressure readout of the devices of the intervention group would be skipped then until the next visit at the center.

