In addition to our main research question on the effect of combined ASA and blood pressure lowering therapy, a secondary aim is to study the effect of the blood pressure component of the combination therapy. For this aim we will accurately record who is using intensive blood pressure lowering therapy. Data of both the intervention and the control arms of PROTECT-U can be used for this purpose. For this research aim we will relate the intensive blood pressure lowering therapy usage percentage to the primary outcome. As this analysis pertains to a non-randomized comparison we need to adjust for potential confounding by other determinants of the primary outcome, including the other component (acetylsalicylic acid) of the combined treatment. Analyses will be done with multivariable Poisson regression in which we will model cumulative incidence of the primary outcome at three years.

We will do an additional analysis restricted to the patients randomized to the intervention group, because within this group detailed data on achieved blood pressure will be available obtained with a device that transmits blood pressure to a central post. For each patient we will calculate the percentage of time that systolic blood pressure is below 120 mm Hg. Then we will do an

analysis similar as described above in which we will relate the percentage of time that systolic blood pressure is below 120 mm Hg to the primary outcome, also adjusted for other determinants of the outcome.

Another secondary aim is to study the effect of ASA treatment alone. For these analyses, we will use data on drug accountability (for acetylsalicylic acid use). As these analyses pertain to non-randomized comparisons, we need to adjust for potential confounding by other determinants of the primary outcome, including the other component of the combined treatment. Analyses will be done with multivariable Poisson regression in which we will model cumulative incidence of the primary outcome at three years. These data will not be subject to an interim analysis.

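### Home readings at up to four a week do not stay within 100 per follow-up, as section 6.2 says they will: an on-time six-month visit gives about 104

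*Protocol*

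**What the plan says.** Section 6.2 (Baseline Visit) gives intervention patients a home device and recommends that they "measure blood pressure at home at least once per week and up to 4 times per week". It presents this as a safeguard: "which will ensure that we do not exceed the maximum of 100 measurements at the time of each follow-up". The same section adds that missing the weekly measurement is not a protocol deviation.

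Section 6.3 (Treatment Visits) sets "post-randomization visits, at month 6 (+/- 30 days), and every 6 months (+/- 30 days) thereafter". Intervention patients bring the device to the visit, "to permit a readout of the blood-pressure values to a tablet computer at the trial centre". There is a second transfer route, because the investigator transmits readings "In case patients did not yet transfer the blood pressure measurements to the central database using their own smartphone". If Covid-19 forces a telephone visit instead, "The blood pressure readout of the devices of the intervention group would be skipped then until the next visit at the center".

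The readings have two uses. Sections 2.3 and 6.3 describe a graph of pressures over the past six months, from which the investigator judges whether the target is met. Section 9.3 plans an additional analysis within the intervention group: "For each patient we will calculate the percentage of time that systolic blood pressure is below 120 mm Hg". That percentage is then related to the primary outcome.

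**The concern.** The sentence in 6.2 is a guarantee, and it can be checked against the visit schedule in the next section. Six months is slightly more than 26 weeks, so four readings a week pass 100 even when the visit is on time. The visit windows and the skipped-readout rule lengthen the interval further.

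The protocol itself treats 100 as a ceiling and links the recommended frequency to it. If readings above the ceiling are not kept, the gap would fall on the patients who measure most often and at one end of the interval between readouts. It would reach the graph used at the visit and the percentage-of-time variable in 9.3.

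**Working it through.** **Inputs.** Upper frequency 4 per week and limit 100 (6.2). Visits every 6 months, window 30 days either side (6.3). Readout deferred to the next centre visit after a Covid-19 telephone visit (6.3). Six calendar months are taken as 365.25 / 2 = 182.6 days.

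**Formula.** Readings = rate per week × days between readouts / 7, with no transfer in between.

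**When the stated limit would hold.** 100 / 4 = 25 weeks = 175 days. The guarantee therefore holds only if the interval is 175 days or shorter. Counting a month as four weeks gives 24 weeks × 4 = 96, which would fit. Other usual readings of six months do not: 180 days gives 102.9, 26 weeks gives 104 and six calendar months give 104.4.

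**Counts under the schedule in 6.3**

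| Interval between readouts | Days | Weeks | 1 per week | 2 per week | 3 per week | 4 per week |
|---|---|---|---|---|---|---|
| One visit 30 days early | 152.6 | 21.8 | 21.8 | 43.6 | 65.4 | 87.2 |
| On time | 182.6 | 26.1 | 26.1 | 52.2 | 78.3 | 104.4 |
| One visit 30 days late | 212.6 | 30.4 | 30.4 | 60.8 | 91.1 | 121.5 |
| Early visit, then late visit | 242.6 | 34.7 | 34.7 | 69.3 | 104.0 | 138.6 |
| One readout skipped | 365.25 | 52.2 | 52.2 | 104.4 | 156.5 | 208.7 |

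**Which rows apply when.** The first interval starts at baseline, so its longest value within the windows is 212.6 days, or about 122 readings. The row with about 139 needs a later interval, with one visit 30 days early and the next 30 days late. It also takes the windows as counted from randomisation. If they were counted from the previous visit, about 122 would be the maximum throughout.

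**Who exceeds the limit.** On time, the break-even rate is 100 / 26.1 = 3.8 per week, so only patients near the top of the recommended range pass 100. Within the windows, once or twice a week gives at most 69, and three times a week passes 100 only at the longest interval (104). After one skipped readout the break-even rate falls to 100 / 52.2 = 1.9 per week, so patients measuring twice a week pass it as well. These rates describe where the limit is crossed; they are not proposed frequencies.

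**The case against.** Several points on the other side are sound.

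- **The protocol does not describe data loss.** It never says whether 100 refers to device memory, a transfer batch or a display, or what happens to reading 101. A reader might turn the counts into lost shares, for example 1 − 100/104.4 = 4% on time or 1 − 100/208.7 = 52% after a skipped readout. The documents support the counts but not the losses.
- **There is another transfer route.** Section 6.3 mentions transfer by the patient's own smartphone, with the investigator transmitting whatever has not yet been sent. If that stores the readings centrally, no harmful build-up occurs for patients who use it. This stands, but no section requires the transfer or ties it to a reading count or a skipped readout.
- **Few patients need be affected.** The frequency is a recommendation starting at once a week.
- **The use is secondary.** The analysis in 9.3 is additional, non-randomised and confined to the intervention group. Seated pressure is recorded separately at treatment visits.

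A reader might also infer that the percentage of time at target is biased upwards, because the early weeks before pressure has come down would be overwritten. That needs a storage rule that the protocol does not give; a device that stops storing when full would lose the latest weeks instead. The count of about 139 cannot be used in that argument, because it cannot arise in the first interval.

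Finally, a reader might conclude that the recommended frequency should be capped at a lower value. Home measurement is part of the randomised strategy, so that would change the intervention, and the arithmetic does not require it. How to weight readings over calendar time is detail for the statistical analysis plan and is not an error here.

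**Conclusion.** The guarantee in 6.2 is wrong as written. At the highest frequency it recommends, the schedule in 6.3 gives about 104 readings on time, about 122 with one visit 30 days late, about 139 in a later interval from an early to a late visit, and about 209 after a skipped readout. These counts assume sustained measurement at four a week and no transfer between readouts; the figure of 139 also assumes windows anchored to randomisation.

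Any consequence is conditional. If the limit is device memory, readings from the most frequent measurers who do not transfer early could be missing from the six-month graph and from the percentage-of-time analysis. After a skipped readout this extends to patients measuring about twice a week. The size and direction of any effect cannot be derived from the protocol. The primary endpoint and the randomised comparison are not affected. This is a low-priority correction.

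**What to change.** In 6.2, reconcile the stated frequency, the visit windows and the limit of 100, and remove the claim that the limit cannot be exceeded. Say what the limit refers to and how readings above it are handled.

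In 6.2 and 6.3, require a data transfer, by smartphone or at the centre, before 100 readings accumulate and whenever a centre readout is skipped. This protects the readings without altering how often patients measure, and no new frequency is proposed.

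The cost is a few sentences, an update to the patient instruction and a reminder to transfer data.
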